#### 8.3.6

Infection rate will be summarized by frequencies and percentages.

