## 2.5 Blinatumomab toxicity profile

The toxicity profile of blinatumomab has been largely consistent with historical studies, with fever, chills, and hypogammaglobulinemia occurring frequently. Tremor, headache, and other mental status changes (e.g., confusion) have been reported. Fever, chills, and other constitutional symptoms are thought to be due to a cytokine release syndrome that occurs shortly after the start of therapy and are reduced with the use of steroids (e.g. dexamethasone 8-24 mg daily x 2-3 days). The adverse effects coincided with a rapid rise in activated T-cells after blinatumomab initiation, essentially confirming the hypothesis (22). Life-threatening neurologic adverse events were uncommon and generally reversible, but seizures have been observed in both the MRD and the active disease studies. Corticosteroids before the first dose and prior to dose escalation ameliorate some of the toxicities.

The adverse reactions in pediatric patients treated with blinatumomab were similar to those seen in adult patients with relapsed or refractory B-cell precursor ALL. Adverse reactions that were observed more frequently in the pediatric population compared to the adult population were pyrexia (80% vs. 61%), hypertension (26% vs. 8%), anemia (41% vs. 24%), infusion-related reaction (49% vs. 34%), thrombocytopenia (34% vs. 21%), leukopenia (24% vs. 11%), and weight gain (17% vs. 6%). In infants and children < 2 years of age, the incidence of neurologic toxicities was not significantly different than for the other age groups, but its manifestations were different (agitation, headache, insomnia, somnolence, and irritability). In the phase I/II open label blinatumomab study in pediatric patients with relapsed / refractory ALL, among the 70 pediatric patients treated on the trial, the most frequent grade 3 adverse events were anemia (36%), thrombocytopenia (21%), and hypokalemia (17%). Three patients (4%) and one patient (1%) had cytokine-release syndrome of grade 3 and 4, respectively. Two patients (3%) interrupted treatment after grade 2 seizures. Reports of compassionate use of blinatumomab in pediatric patients with relapsed / refractory ALL and prior ASCT have shown that blinatumomab did not induce nor exacerbate acute graft versus host disease (24, 25).

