#### 3.1.2 Blinatumomab dosage, administration, and schedule

Blinatumomab is administered as a continuous intravenous infusion (CIV). A single cycle of blinatumomab treatment is 4 weeks of CIV. Since patients are either in remission, or have minimal residual disease at time of treatment, the dosing schedule for minimal residual disease will be followed. Additionally, since both children and adults will be treated on this study, dosing will be weight- and BSA-based as per FDA guidelines for this drug. Please see section 5.3 for details of dosing administration.

The drug administration should not be interrupted, if possible. In case of infusion interruption, due to any technical or logistic reason, the interruption should be as short as possible and the infusion continued at the earliest time possible. Every interruption longer than 1 hour should be documented. If the interruption is longer than 4 hours, re-start of the infusion should be performed under healthcare supervision. The patient should be observed overnight for possible side effects after the restart in the hospital. Administration of dexamethasone premedication as described in Table 3 is recommended. If possible, the infusion duration before and after an interruption should total 28 days per treatment cycle.

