## 4.0 Patient Eligibility

### 4.1 Inclusion Criteria:

1. Patients 1-70 years of age.
2. Patients with B-lineage ALL in a) hematologic complete remission (CR) beyond CR1 at time of transplant; b) primary induction failure defined as requiring more than one line of induction therapy; c) positive minimal residual disease defined by positive flow >0.01% before or after transplant; or d) high risk cytogenetic or molecular features consisting of Ph-like phenotype, detection of BCR-ABL transcript by PCR with a sensitivity of 1/10,000, or detection of the t(9;22) translocation in any metaphases by cytogenetics at time of transplant, or presence of the MLL gene before or after transplant.
3. Received an allogeneic HCT within the last 100 days. Enrollment within 30-100 days after transplant, and after adequate recovery of counts defined as ANC  $\geq 0.5 \times 10^9/L$  without daily use of myeloid growth factor and platelet  $> 20 \times 10^9/L$  without platelet transfusion within 1 week, and adequate organ function to receive blinatumomab defined as creatinine clearance greater than 30 ml/min (or greater than 60 ml/min/1.73), ALT/AST  $< 5 \times$  ULN and serum bilirubin  $< 3 \times$  ULN.
4. Performance status of 0, 1, or 2. Karnofsky (or Lansky for subjects < 16 years old) performance status  $\geq 50$ .

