## 5.0 Treatment Plan

5.1 This is an open-label, single-arm, phase II clinical study.

5.2 All patients will be registered through Core. All of the enrolled subjects' concomitant medications will be collected and readily available in the MDACC electronic medical record and will not be entered into the CRF.

5.3 Patients will receive blinatumomab as continuous intravenous infusion over 4 weeks.

Since this study includes children and adults, dosing will be weight and BSA-based as per FDA approved dosing guidelines:

**For patients  $\geq 45$  kg**, the dose is 28 mcg/day administered as a continuous infusion on days 1-28 of each cycle.

**For patients  $< 45$  kg** the dose is 15 mcg/m^2/day (maximum 28 mcg/day) administered as a continuous infusion on days 1-28 of each cycle

All patients will receive 4 cycles of blinatumomab, with first cycle administered within the first 3 months following HCT, and then at 6 (+/- 2 weeks), 9 (+/- 2 weeks), and 12 (+/- 2 weeks) months following HCT (day of hematopoietic progenitor cell infusion). This schedule was selected to allow for treatment with blinatumomab during the one year following transplant when patients are at risk for relapse while the GVL effect is maturing and becoming robust.

5.4 GVHD prophylaxis will be as institutional standard.

5.5 CNS prophylaxis will be as institutional standard. However, craniospinal radiotherapy for prophylaxis post HCT is not permitted.

5.6 Tyrosine kinase inhibitor (TKI) use for patients with Ph+ ALL will be left to the investigator's discretion.

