#### 8.3.4 Safety Measures

Safety will be assessed by vital signs, laboratory assessments, adverse events, and serious adverse events for all treated patients. Categorical measures will be summarized using frequencies and percentages while continuous variables will be summarized using mean, standard deviation, median, minimum, and maximum.

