## 9.0 Reporting Requirements

### 9.1 Treatment periods

Active treatment period is defined from the first day of treatment administration through 30 days after last dose given. The intensity of adverse events (AE) will be assessed according to the Common Terminology Criteria v4.0 (CTCAE). Adverse events and protocol deviations will be reported accordingly to MDACC policy and procedures. Collection of adverse events will reflect the onset and resolution date and maximum grade. Intermittent events should be labeled as such and followed until resolution. If a patient is taken off study while an event is still ongoing, this will be followed until resolution unless another therapy is initiated. Pre-existing medical conditions will be recorded only if an exacerbation occurs during the active treatment period. Co-morbid events will not be scored separately.

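### Section 8.3.6 plans only a crude infection percentage with no stated window, which would understate full-course risk for patients who stop early while alive and relapse-free

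*Combined protocol and SAP*

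**What the plan says.** Section 8.3.6 reads, in full: "Infection rate will be summarized by frequencies and percentages". It does not give the period covered, the unit (patients or episodes), the denominator or the treatment of patients observed for less time. The general safety paragraph, 8.3.4, supplies a population but no time adjustment: "Safety will be assessed by vital signs, laboratory assessments, adverse events, and serious adverse events for all treated patients", again summarised by counts and percentages.

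The only safety period the document defines is in section 9.1: "Active treatment period is defined from the first day of treatment administration through 30 days after last dose given". Its length depends on how many cycles a patient receives. Section 3.1.2 says "A single cycle of blinatumomab treatment is 4 weeks of CIV". Section 5.3 says "All patients will receive 4 cycles of blinatumomab, with first cycle administered within the first 3 months following HCT". It places the other three cycles about half a year, nine months and one year after transplant, each with a two-week margin on either side. Section 4.1 sets "Enrollment within 30-100 days after transplant". Sections 3.3 and 7 allow treatment to end permanently before the fourth cycle. Section 7.1 closes the study at 1 year without saying from which date.

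For two other events that depend on time, the plan uses a different method. Section 8.2 analyses GVHD by cumulative incidence, with relapse and death as competing risks and censoring at last follow-up. Section 8.3.3 analyses non-relapse mortality by cumulative incidence, with relapse as the competing risk.

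**The concern.** A simple percentage estimates the risk over a course of treatment only if everyone is observed for that course, or if observation ends only in an event that itself closes the risk. Here some patients may leave after one cycle for toxicity, alive and in remission, with most of the year unobserved. They count as full members of the denominator but contribute infections from a short window only.

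Infection matters for this drug after transplant. Section 2.5 describes the toxicity profile as one "with fever, chills, and hypogammaglobulinemia occurring frequently", and Tables 3 and 4 do not list immunoglobulin levels among the scheduled tests. A percentage that falls as discontinuation for toxicity rises could be read as reassurance about a four-cycle regimen that many patients did not complete.

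**Working it through.** The documents give no infection rate, target or discontinuation rate, so there is no planned figure to reproduce. The check has three parts.

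**1. Length of the section 9.1 window.** Inputs: a cycle of 28 days (3.1.2); 30 days after the last dose (9.1); enrolment from day 30 to day 100 after transplant (4.1); cycle 4 at 12 months ± 2 weeks, taken as day 365 ± 14 (5.3). One month is 30.44 days. Section 5.3 puts cycle 1 within 3 months, which does not coincide with the day-100 limit in 4.1, so both are shown.

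Window = start day of last cycle + 28 + 30 − day of first dose.

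| Pattern | Calculation | Days | Months |
|---|---|---|---|
| One cycle | 28 + 30 | 58 | 1.9 |
| Four cycles, first dose day 30 | 365 + 58 − 30 | 393 | 12.9 |
| Four cycles, first dose day 90 | 365 + 58 − 90 | 333 | 10.9 |
| Four cycles, first dose day 100 | 365 + 58 − 100 | 323 | 10.6 |
| Shortest four-cycle window | 351 + 58 − 100 | 309 | 10.2 |
| Longest four-cycle window | 379 + 58 − 30 | 407 | 13.4 |
| Cut at 1 year after transplant | 365 − 100 to 365 − 30 | 265 to 335 | 8.7 to 11.0 |

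The ratio of the four-cycle to the one-cycle window is 309/58 = 5.3 to 407/58 = 7.0. Under the 1-year cut it is 265/58 = 4.6 to 335/58 = 5.8.

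**2. Which early stoppers create a gap.** Compare the crude percentage with a cumulative incidence of first infection that treats death and relapse as competing events.
- Stopped by relapse or death: the competing-risks estimate assigns no later infection to this patient. If nobody is otherwise censored, it equals the simple proportion with an infection before relapse or death. These patients add nothing to the gap.
- Stopped alive and relapse-free without an infection: the patient is still at risk but unobserved. The crude percentage counts the patient as infection-free, whereas the cumulative incidence censors the patient.
- Stopped after an infection: already counted in both.

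**3. Illustrative size.** Let F be the full-course cumulative incidence over 335 days, and P58 the part of it accrued by day 58. Let f be the share of patients whose observation ends at 58 days while alive and relapse-free. F and f are assumptions, as is equal later risk in stoppers and non-stoppers.

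Crude = (1 − f) × F + f × P58, so shortfall = f × (F − P58).

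Constant hazard: P58 = 1 − (1 − F)^(58/335). Front-loaded hazard (Weibull, shape 0.5): P58 = 1 − (1 − F)^√(58/335).

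For F = 50%, P58 is 11.3% (constant) or 25.1% (front-loaded). With f = 40%, crude is 0.6 × 50 + 0.4 × 11.3 = 34.5%, or 0.6 × 50 + 0.4 × 25.1 = 40.0%.

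| F | Hazard | P58 | Shortfall in points, f = 10% | f = 20% | f = 40% |
|---|---|---|---|---|---|
| 30% | constant | 6.0% | 2.4 | 4.8 | 9.6 |
| 30% | front-loaded | 13.8% | 1.6 | 3.2 | 6.5 |
| 50% | constant | 11.3% | 3.9 | 7.7 | 15.5 |
| 50% | front-loaded | 25.1% | 2.5 | 5.0 | 10.0 |
| 70% | constant | 18.8% | 5.1 | 10.2 | 20.5 |
| 70% | front-loaded | 39.4% | 3.1 | 6.1 | 12.2 |

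The shortfall is proportional to f and vanishes as f goes to zero.

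**The case against.** The strongest reply is that the unequal window is not written into the infection analysis. Section 8.3.6 does not refer to section 9.1. Section 9.1 uses the active treatment period explicitly only when deciding whether to record worsening of pre-existing conditions, and does not say that adverse event collection stops there. Section 9.4 lists prolonged hospitalisation for infection as serious, with no end date. This stands: what can be documented is an unstated window, and the 58-day figure is conditional on the most natural reading. The omission is still worth correcting, because without a window the percentage has no defined meaning.

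A second reply is that the consequence is small. Infection is in no objective in section 1, is not a feasibility parameter in 8.2 and is not named in the stopping rule in 8.3.5. With 30 patients and a true 50%, the standard error alone is √(0.5 × 0.5/30) = 9.1 points, larger than many of the shortfalls above. This also stands and sets the severity, although sampling error is shown by an interval and a shortfall in one direction is not.

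Three stronger readings are tempting and not supported. A reader might infer that everyone who stops early pulls the percentage down; patients who stop for relapse or death do not, measured against the competing-risks estimate that is the right comparator. A reader might infer that four-cycle patients are always observed for more than 11 months; the dates give 10.2 to 13.4 months, or 8.7 to 11.0 under one reading of section 7.1. A reader might infer that the plan discards repeat infections; 8.3.6 does not name its unit, so it neither counts nor excludes them.

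**Conclusion.** The point holds in a limited form. Section 8.3.6 states no window and makes no allowance for unequal observation. If infections are collected over the section 9.1 period, observation differs about five- to seven-fold between one-cycle and four-cycle patients (4.6- to 5.8-fold under the 1-year cut). The crude percentage then understates full-course risk. The direction is secure, because a shorter window can only miss infections.

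The size cannot be given from the documents. It depends on how many patients stop early alive and relapse-free, and on how early infections cluster. It is smaller if infection itself is the reason for stopping. The illustrated 1.6 to 20.5 points rest on assumed values of F (30% to 70%) and f (10% to 40%) and are not a prediction for this trial.

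The fault affects the interpretation of one descriptive safety result. It does not touch the sample size, the stopping boundaries or the feasibility conclusion. Severity is minor: desirable, not necessary.

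**What to change.** In section 8.3.6:

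- State the infection window as first dose to the end of the section 9.1 period, and say how the 1-year limit in 7.1 applies to it. State the unit and the denominator.
- Report the cumulative incidence of first infection from first dose, with death and relapse as competing events and censoring at the end of each patient's adverse event collection. This follows the approach already used in 8.2 and 8.3.3.
- Report first infections per 100 patient-months at risk with an exact 95% confidence interval. Count repeat episodes only if they are recorded as separate events. Section 9.1 asks for intermittent events to be labelled as such and for co-morbid events not to be scored separately, so episode counts may not be recoverable.
- Keep the crude percentage as a descriptive column.

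The cost is a few lines of SAP text and slightly more analysis. Onset dates are already collected under 9.1, and 9.3 does not name infection among the events left uncollected, so time to first infection should need no new data. One limitation should be stated with the result: when toxicity causes stopping, censoring may be informative, so the bias is reduced but not necessarily removed.

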**Table 5. Stopping Boundaries**

Total number of patients	Stop if this many patients have toxicity:
1-4	Never stop with this many patients
5	3-5
6-7	4-7
8-10	5-10
11-13	6-13
14-16	7-16
17-18	8-18
19-21	9-21
22-24	10-24
25-27	11-27
28-29	12-29
30	Always stop with this many patients

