#### 8.3.5 Continuous Toxicity Monitoring

Continuous monitoring of toxicity will be assessed for all treated patients, beginning with the first cohort of five patients. Assuming a prior beta distribution of (0.6, 1.4), the study will terminate if the  $\Pr(\delta_t > 0.30 | \text{data}) > 0.85$ , where  $\delta_t$  is the toxicity rate attributable to the treatment. Toxicities are defined as any 1) grade 3-4 acute GVHD greater than 30%, 2) secondary graft failure >30%, or 3) NRM within one cycle of blinatumomab (i.e., 30 days). The decision rule for terminating for toxicity is presented in Table 5 and the operating characteristics for this rule are presented in Table 6. The method used to produce the decision rule and operating characteristics was designed by Thall, Simon, and Estey (1995).

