**Table 6. Operating Characteristics**

True % of DLTs	Pr (stopping early)	Median Sample Size (interquartile)
0.10	0.01	30 (30, 30)
0.20	0.10	30 (30, 30)
0.30	0.36	30 (13, 30)
0.40	0.72	13 (5, 30)
0.50	0.94	5 (5, 13)

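### Table 5 has no stop before patient 5, even when three toxicities in the first three or four patients already make stopping at 5 certain

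*Combined protocol and SAP*

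**What the plan says.** Section 8.3.5 (Continuous Toxicity Monitoring) gives the toxicity rate a Beta(0.6, 1.4) prior and ends the study when the posterior probability of a rate above 0.30 exceeds 0.85. On timing it says "Continuous monitoring of toxicity will be assessed for all treated patients, beginning with the first cohort of five patients".

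Table 5 puts this into counts. For 1-4 patients the entry is "Never stop with this many patients". At 5 patients the study stops with 3-5 toxicities, at 6-7 with 4 or more, and so on up to 12 or more at 28-29. The row for 30 patients, the planned maximum, reads "Always stop with this many patients". Table 6 gives the probability of early stopping and the median and quartiles of sample size at true rates from 0.10 to 0.50.

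No other trial-level halt before patient 5 is described. Section 7 covers removal of individual patients. Section 9.4 sends serious adverse events to the principal investigator, who notifies the IRB, but it sets no pause in accrual. Under Section 8.2, the primary objective is met if the trial finishes without reaching a stopping rule.

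**The concern.** If the first three patients, or three of the first four, have a toxicity, the count at patient 5 will be at least 3 whatever happens next. The trial must then stop at 5 and the primary objective in Section 8.2 cannot be met. Table 5 nevertheless gives no stop at 3 or 4 patients. Read literally, it gives none even after four non-relapse deaths in four patients.

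The counted events are grade 3-4 acute GVHD, secondary graft failure, and non-relapse mortality within one cycle. Section 3.1.2 describes the patients as in remission or with minimal residual disease. Up to two more of them could be exposed to a regimen whose termination is already settled, with nothing gained for the stopping decision.

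**Working it through.** **Inputs.** Prior Beta(0.6, 1.4), rate limit 0.30, posterior cut-off 0.85 and first look at five patients (Section 8.3.5); boundaries and maximum of 30 (Table 5); stated operating characteristics (Table 6). Each patient counts as having a toxicity or not, as Table 5 does, and each outcome is taken as known before the next patient is treated.

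**Step 1: reproduce Table 5.** After x toxicities in n patients the posterior is Beta(0.6 + x, 1.4 + n − x). The boundary is the smallest x for which Pr(rate > 0.30) exceeds 0.85. At n = 5 the posterior probability is 0.626 for x = 2 and 0.875 for x = 3, so the boundary is 3. All entries from n = 5 to n = 29 match Table 5.

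**Step 2: reproduce Table 6.** Exact binomial recursion, applying Table 5 after every patient from 5 to 29, gives early-stopping probabilities of 0.0103, 0.0966, 0.3576, 0.7184 and 0.9384 at true rates 0.10 to 0.50. These round to the stated 0.01, 0.10, 0.36, 0.72 and 0.94. All medians and quartiles agree too.

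**Step 3: apply the same criterion below five patients.**

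| Toxicities / patients | Pr(rate > 0.30) | Stop at 5 already certain? |
|---|---|---|
| 1/1 | 0.789 | no |
| 2/2 | 0.928 | no |
| 2/3 | 0.838 | no |
| 3/3 | 0.976 | yes |
| 2/4 | 0.734 | no |
| 3/4 | 0.935 | yes |
| 4/4 | 0.992 | yes |

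The plan's own criterion therefore gives a boundary of 3 at both n = 3 and n = 4.

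**Step 4: how often, and how many patients.** With true rate p:

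- Three toxicities in the first three: p³. Two patients saved.
- Third toxicity at patient 4: 3p³(1 − p). One patient saved.
- Stopping certain before patient 5: p³ + 3p³(1 − p).
- Expected saving: 2p³ + 3p³(1 − p).

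At p = 0.40: p³ = 0.064 and 3 × 0.064 × 0.6 = 0.1152. The chance is 0.1792 and the expected saving is 0.128 + 0.1152 = 0.2432.

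| True rate | 3 of 3 | Certain before patient 5 | Expected saving |
|---|---|---|---|
| 0.10 | 0.1% | 0.4% | 0.005 |
| 0.20 | 0.8% | 2.7% | 0.035 |
| 0.30 | 2.7% | 8.4% | 0.11 |
| 0.40 | 6.4% | 17.9% | 0.24 |
| 0.50 | 12.5% | 31.3% | 0.44 |
| 0.60 (beyond Table 6) | 21.6% | 47.5% | 0.69 |

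**Step 5: effect on Table 6.** With a boundary of 3 added at n = 3 and 4, the early-stopping probabilities are again 0.0103, 0.0966, 0.3576, 0.7184 and 0.9384. They cannot change, because every path stopped early would have stopped at 5. Mean sample size falls from 29.751 to 29.746, 27.88 to 27.85, 22.95 to 22.83, 15.98 to 15.74 and 10.24 to 9.81. The one printed figure that moves is the lower quartile at 0.50: the probability of having stopped by patient 4 becomes 0.3125, above 0.25, so the quartile goes from 5 to 4. At 0.40 that probability is 0.1792, so the quartile stays at 5.

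**The case against.** The five-patient start is stated openly, and Section 8.3.5, Table 5 and Table 6 agree with one another. On this point there is no error or contradiction. That is correct, and it makes this a refinement of a design choice.

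The gain is also small: 0.11 patients on average at the limiting rate of 0.30, and two patients only after 3 of 3, which has probability 2.7% there. These savings are upper bounds. Section 8.3.5 gives non-relapse mortality a 30-day window and states none for GVHD or graft failure, and the plan describes no pause between patients. Patients 4 and 5 may already be on treatment when the third toxicity is known. This limits the size of the benefit, but Table 6 rests on the same assumption of immediate outcomes.

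Table 5 does not oblige anyone to enrol patients 4 and 5, and the investigator or IRB, who would hear of deaths and graft failures under Section 9.4, could halt the trial. The accurate claim is that the pre-specified rule contains no stop before patient 5. A discretionary halt does not replace one.

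Finally, 2/2 also exceeds the posterior limit (0.928), so the posterior argument might seem to require stopping there too. The difference is certainty. After 2/2, the boundary at 5 is met only if at least one of the next three patients has a toxicity, which has probability 1 − 0.7³ = 0.657 at a true rate of 0.30. Looks from patient 1 would also raise early stopping to 0.0175, 0.1145 and 0.376 at rates 0.10, 0.20 and 0.30. Leaving 2/2 out keeps the stated error rates intact.

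**Conclusion.** The concern holds. After 3/3 or 3/4 the stop at 5 is unavoidable, the plan's posterior criterion is already met, and Table 5 still provides no stop. The benefit of closing the gap is modest: at most two patients in one trial, and 0.11 to 0.44 on average at true rates of 0.30 to 0.50. It has no statistical cost. The size rests on two assumptions: toxicities are counted per patient, although Section 8.3.5 attaches percentages to two of the three components, and outcomes are known before the next patient is treated. Slower reporting would shrink the saving but would not make the change harmful. The sponsor should make it.

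**What to change.** - **Table 5:** replace the 1-4 row with two rows: 1-2 patients, no stopping; 3-4 patients, stop if 3 or more have toxicity.
- **Section 8.3.5:** replace "beginning with the first cohort of five patients" with a statement that the rule applies from the third treated patient, using the boundaries in Table 5.
- **Table 6:** change the sample-size entry at 0.50 from 5 (5, 13) to 5 (4, 13).

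The cost is one table row, one sentence and one figure. The risk of stopping wrongly, the probability of stopping a toxic regimen and the maximum of 30 patients do not change. The new boundary follows from the existing limit at five patients and the existing 0.85 criterion, so no new threshold is introduced.
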